2.6.1.1.1 AE reporting for CT.gov and EudraCT

For the legal requirements of clinicaltrials.gov and EudraCT, two required tables on treatment emergent adverse events which are not serious adverse events with an incidence greater than X% (where X lies between 0-5 %, will be decided later) and on treatment emergent serious adverse events and SAE suspected to be related to study treatment will be provided by system organ class and preferred term on the safety set population.

If for a same patient, several consecutive AEs (irrespective of study treatment causality, seriousness and severity) occurred with the same SOC and PT:

- a single occurrence will be counted if there is ≤ 1 day gap between the end date of the preceding AE and the start date of the consecutive AE
- more than one occurrence will be counted if there is > 1 day gap between the end date of the preceding AE and the start date of the consecutive AE

For occurrence, the presence of at least one SAE / SAE suspected to be related to study treatment / non SAE has to be checked in a block e.g., among AE's in a ≤ 1 day gap block, if at least one SAE is occurring, then one occurrence is calculated for that SAE.

The number of deaths resulting from SAEs suspected to be related to study treatment and SAEs irrespective of study treatment relationship will be provided by SOC and PT.

2.6.1.2 Laboratory data

All laboratory samples will be processed through the central laboratory. Laboratory data consist of hematology and biochemistry including peripheral blood eosinophils.

Laboratory data measured more than 7 days after last dose of study treatment are regarded as post-treatment data and will not be summarized. All data will be included in the analyses regardless of rescue medication use. All data will be listed.

The number and percentage of patients with newly occurring or worsening laboratory abnormalities meeting the clinically notable criteria (see [Section 5.4](#) for definition of notable values) summarized by cohort, laboratory parameter at any time on treatment considering all post-baseline data from scheduled, unscheduled and premature discontinuation visits.

For a patient to meet the criterion of a newly occurring clinically notable value, the patient needs to have a baseline value that is not clinically notable for that parameter. For a patient to meet the criterion of a worsening clinically notable value, the patient needs to have a baseline value that is clinically notable and also have a worse post-baseline value. For patients with missing baseline value, any post-baseline notable value will be considered as newly occurring. A listing of all patients with notable laboratory values will be provided.

For summary tables on laboratory parameters considering values, which are lower or greater than the limit of quantification, the following approach will be taken. For values which are flagged as lower than the lower limit of quantification, the values presented in summary tables should be multiplied by 0.5 and for values which are flagged as greater than upper limit of quantification as 1.5, the values presented in summary tables should be multiplied by 1.5.

Laboratory data, if collected in local LAB CRF page, will be listed only as appropriate.

2.6.1.3 ECG

ECG measurements include ventricular rate, QT interval, RR interval, PR interval, QRS duration, and Fridericia's QTc (calculated as $QTcF = QT / \sqrt[3]{RR}$ (in seconds), where $\sqrt[3]{}$ denotes the cube root).

ECG data measured more than 7 days after last dose of study treatment are regarded as post treatment data and will not be summarized. All data will be included in the analyses regardless of rescue medication use. All data will be listed.

- The number and percentage of patients with newly occurring or worsening notable QTcF values (see [Section 5.5](#) for definition of notable values) summarized by cohort at any time on treatment considering all post-baseline data from scheduled, unscheduled and premature discontinuation visits

The same approach as for notable laboratory values will be used to define a newly occurring notable QTc value and a worsening notable QTc value.

2.6.1.4 Vital signs

Vital signs measurements include body temperature, systolic and diastolic blood pressure (SBP and DBP) and pulse rate.

Vital signs data measured more than 7 days after last dose of study treatment are regarded as post-treatment data and will not be summarized. All data will be included in the analyses regardless of rescue medication use. All data will be listed.

The number and percentage of patients with newly occurring or worsening notable vital signs values (see [Section 5.5](#) for definition of notable values) summarized by cohort, parameter at any time on treatment considering all post-baseline data from scheduled, unscheduled and premature discontinuation visits

The same approach as for notable laboratory values will be used to define a newly occurring notable vital sign value and a worsening notable vital sign value.

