#### **Vital signs**

Vital signs measurements include body temperature, systolic and diastolic blood pressure (SBP and DBP) and pulse rate. Summary statistics will be provided by cohort and visit/time-point.

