## 16 Appendices

### 16.1 Appendix 1: Clinically notable laboratory values and vital signs

There are no specific notable range criteria for this study; however, the Central Laboratory will flag laboratory values falling outside of the normal range on the Central Laboratory Report (which the investigator should sign off) and the investigator will report any values considered clinically significant in the eCRF.

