2.1.1.3 Post-baseline measurement

Post-baseline measurements are defined as those assessments after the first dose of study treatment. When change from baseline is of interest the following formula will be used for each scheduled visit and time-point where baseline and post-baseline values are both available: Change from baseline = post-baseline value – baseline value.

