15	81%- 124%	78%- 128%	76%- 131%	74%- 135%	72%- 138%	70%- 142%	69%- 145%	67%- 149%	66%- 152%	64%- 156%
16	81%- 123%	79%- 126%	77%- 130%	75%- 133%	73%- 136%	71%- 140%	70%- 143%	68%- 147%	67%- 150%	65%- 153%
17	82%- 122%	80%- 125%	78%- 128%	76%- 132%	74%- 135%	72%- 138%	71%- 141%	69%- 144%	68%- 147%	66%- 151%
18	83%- 121%	81%- 124%	79%- 127%	77%- 130%	75%- 133%	73%- 136%	72%- 140%	70%- 142%	69%- 145%	67%- 148%

For example, if we observe a CV% of 55% in the interim data, then 12 subjects are required to complete treatment with the high dose and to provide the planned PK samples to give ~80% probability for the 95% confidence intervals (CI) of geometric means of QAW039 AUC0-

24h,ss to fall approximately within the range of (68%U, 147%U). The sample size for the high dose can vary from 6 to 18 subjects, so that total number of subjects completing treatment (75 mg or high dose) and providing planned PK samples is maximum of 24. For example, if we observe a CV% of 80% in the interim data, then 18 subjects will be recruited at the high dose to provide the planned PK samples, though the 95% CI of geometric means of QAW039 AUC0-24h,ss will fall outside the range of (68%U, 147%U).

4 Change to protocol specified analyses

This statistical analysis plan is an abbreviated approach of presenting the limited data collected in the study and does not reflect the full analysis scope described in Section 12 of the study protocol (Version 01, Amendment 1 to original protocol released on 13-Feb-2019).

The following changes to the protocol specified analyses will be done:

- Definition of treatment emergent for safety adjusted: treatment end + 1 day will be replaced by treatment end date + 7 days for laboratory, vital signs, ECG and AEs, and to + 30 days for SAEs, to follow standard of QAW program.

5 Appendix

This appendix gives details about statistical methods in addition to the report text. All analyses will be performed by the most recent version of SAS available in the statistical programming environment.

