5.5 Vital signs and ECG – definition of clinically notable values

The following table shows the clinical notable criteria for vital signs.

Vital sign parameter (unit)	Lower bound of clinically notable range	Upper bound of clinically notable range
Notable value considering newly occurring or worsening cases		
Systolic blood pressure (mmHg)	< 80 (all)	> 150 (all)
Diastolic blood pressure (mmHg)	< 45 (all)	> 105 (all)
Pulse rate (bpm)	< 50 (all)	> 150 (6-8), >130 (9-12)
Notable change from baseline		
Systolic blood pressure (mmHg)	≤ 90 and decrease from baseline by ≥ 15	≥ 140 and increase from baseline by ≥ 15
Diastolic blood pressure (mmHg)	≤ 55 and decrease from baseline by ≥ 15	≥ 95 and increase from baseline by ≥ 15
Pulse rate (bpm)	≤ 60 and decrease from baseline by ≥ 15	≥ 140 and increase from baseline by ≥ 15 (6-8) ≥ 120 and increase from baseline by ≥ 15 (9-12)

The following table shows the clinical notable criteria for QTcF.

ECG parameter (unit)	Clinically notable range
Notable value criterion for newly occurring or worsening cases	
QTc (msec)	> 450 msec for males and females
QTc (msec)	> 500 msec for males and females
Notable change from baseline	
QTc	30 – 60 msec
QTc	> 60 msec

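### The SAP replaces the protocol's descriptive vital-sign and ECG tables with counts of notable values, so a consistent shift below the notable thresholds would appear only in listings, and its list of changes does not say so

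*SAP*

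**What the plan says.** Vital signs and ECG are endpoints of the secondary safety objective in both documents (Protocol Table 2-1, SAP Table 1-1).

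- **Protocol 12.5.1**, vital signs: "Summary statistics will be provided by cohort and visit/time-point". The ECG paragraph makes the same commitment for ventricular rate, QT, RR, PR, QRS and QTcF.
- **SAP 2.6.1.4**, vital signs: one tabulated output, "The number and percentage of patients with newly occurring or worsening notable vital signs values", at any time on treatment, plus "All data will be listed".
- **SAP 2.6.1.3**, ECG: one tabulated output, "The number and percentage of patients with newly occurring or worsening notable QTcF values", also with a full listing.
- **SAP 5.5** defines notable values in two blocks. One holds absolute limits for newly occurring or worsening cases. The other holds changes from baseline, for example "≥ 140 and increase from baseline by ≥ 15" for a systolic rise.
- **SAP 2.1.1.3** gives a formula: "When change from baseline is of interest the following formula will be used for each scheduled visit and time-point".
- **SAP Section 4** repeats that the plan is abbreviated, then itemises a single change: "Definition of treatment emergent for safety adjusted".
- **Protocol 16.1** states: "There are no specific notable range criteria for this study". The vital-sign and ECG bounds that drive the SAP tables therefore come from the SAP alone.

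**The concern.** A count of threshold crossings and a mean with its spread answer different questions. The count looks for individual outliers; the summary shows whether the group moved. The protocol planned the second for these endpoints and the SAP specifies only the first. If every child moved in the same direction by less than the bound, the table would hold zeros and could be read as no effect on blood pressure, pulse or QTcF. This is the first fevipiprant study in children aged 6 to under 12, so these readings are the first of their kind.

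The SAP text suggests that the loss was not fully thought through. The change-from-baseline formula serves no stated vital-sign or ECG table. SAP 5.3 keeps unscheduled readings out of everything except the notable-value summaries and keeps mistimed readings out of by-time-point assessments, yet no section specifies any other summary or any by-time-point assessment of these data.

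**Working it through.** The documents give no figure on this point to reproduce. The check compares the text and then applies the SAP's own bounds.

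**1. Which measurements reach an on-treatment table**

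| Measurement | Protocol 12.5.1 | SAP 2.6.1.3 / 2.6.1.4 with 5.5 |
|---|---|---|
| SBP, DBP, pulse | descriptive, by cohort and time-point | notable count, any time on treatment |
| QTcF | descriptive, by cohort and time-point | notable count, any time on treatment |
| Body temperature | descriptive, by cohort and time-point | no criterion, so listing only |
| Ventricular rate, QT, RR, PR, QRS | descriptive, by cohort and time-point | no criterion, so listing only |

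**2. How large a uniform shift can be and still count as zero**

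Bounds are from SAP 5.5, for whole-number readings. The baselines are assumptions, as the documents give none. A blood-pressure or pulse change counts only if it is at least 15 and also reaches a stated level, so the largest uncounted rise is (change-row level − 1) − baseline. The change rows are assumed to be tabulated.

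| Measurement | Largest uncounted rise, central baseline | Over a range of baselines |
|---|---|---|
| SBP (level 140) | 139 − 100 = 39 | 49 at 90, 29 at 110 |
| DBP (level 95) | 94 − 60 = 34 | 44 at 50, 24 at 70 |
| Pulse, age 6-8 (level 140) | 139 − 90 = 49 | 59 at 80, 39 at 100 |
| Pulse, age 9-12 (level 120) | 119 − 90 = 29 | 39 at 80, 19 at 100 |

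QTcF has no level condition on its 30-60 msec change row, so the largest uncounted rise is the smaller of 29 and 450 − baseline. That is 29 for any baseline up to 421 (421 + 29 = 450, not above 450) and less for higher baselines. A uniform rise of 30 msec puts every child in the table.

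**3. Downward shifts, change rows tabulated**

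- SBP is counted at 90 or below with a fall of at least 15, or below 80. From 100, a fall of 15 gives 85 and is counted; a fall of 14 gives 86 and is not. From 110 the fall must reach 20 (110 − 20 = 90).
- DBP is counted at 55 or below with a fall of at least 15, or below 45. From 60, a fall of 15 gives 45 and is counted.
- Pulse is counted at 60 or below with a fall of at least 15, or below 50. From 90, the fall must reach 30.

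The blind zone is therefore much narrower for falls in blood pressure than for rises. Pulse keeps a wide one in both directions.

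**4. If the change rows are not tabulated**

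SAP 2.6.1.3 and 2.6.1.4 point to the whole of 5.5, which favours counting both blocks. But the output is worded as newly occurring or worsening values, and SAP 2.6.1.2 defines those by whether the baseline value was itself notable. A change criterion has no baseline status, so the wording does not fit that block. With the absolute limits alone, a rise in SBP from 100 to 150, in DBP from 60 to 105, or in QTcF from 405 to 450 would go uncounted, as would a fall in SBP from 100 to 80 (shifts of 50, 45, 45 and 20).

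**5. Who contributes**

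SAP Section 1 says that all of Cohort A (six planned) completed, and that five Cohort B children were treated with none completing. Protocol Table 16-5 schedules blood pressure, pulse and ECG at EOT pre-dose and 2 h. Under SAP 5.3 a discontinuation visit is unscheduled and enters only the notable-value summaries, so restored post-baseline columns would rest essentially on Cohort A.

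No probability of an empty table is given. It would need assumed baselines and standard deviations, and it changes markedly with the direction of the shift and with whether one or both EOT readings count.

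**The case against.** The strongest reply is that this is a declared reduction in scope. The SAP says twice, in Sections 1 and 4, that it is abbreviated and does not cover the full scope of protocol Section 12, and it explains why. Every reading is listed, and with six and five treated children a reader can see the direction of change in the listings. There is no control group and SAP 5.6 plans no inference. Adding notable criteria where the protocol had none supplements the protocol and does not weaken detection. All of this stands, and it limits the point to what is tabulated and what Section 4 itemises.

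It does not remove the point. A general statement of abbreviation does not tell a reader which endpoint summaries were dropped, and Section 4 lists one change as though complete. Early termination does not explain the loss for Cohort A, whose children completed.

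Two stronger readings are tempting and not supported. A reader might infer that any consistent shift in blood pressure, pulse or QTcF would appear in no table. SAP 5.5 has lower bounds and a QTcF change row without a level condition, so many falls in blood pressure and QTcF rises of 30 msec or more would be counted if those rows are used. A reader might also infer that the pre-dose and 2 h readings were scheduled to contrast trough with peak. The documents give only the timetable, not that purpose.

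**Conclusion.** The point holds in limited form. The SAP drops the protocol's descriptive vital-sign and ECG tables and does not itemise the change. A consistent shift below the notable thresholds would be visible only in listings. With the change rows tabulated and the central baselines above, that covers rises of up to 39 mmHg systolic, 34 mmHg diastolic, 49 bpm (age 6-8) or 29 bpm (age 9-12), and 29 msec in QTcF; for falls in blood pressure it is about 14 mmHg. Six measurements (body temperature, ventricular rate, PR, QRS, QT and RR) reach no specified on-treatment table.

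The comparison of the documents needs no assumption. The sizes depend on the assumed baselines and on reading 5.5 as including its change rows. This is a reporting gap: the data are neither concealed nor lost, and the primary PK analysis, sample size and error rates are unaffected.

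**What to change.** 1. In SAP 2.6.1.3 and 2.6.1.4, restore the protocol 12.5.1 tables: n, mean, SD, median, minimum and maximum of the value, by cohort and scheduled time-point, including EOT pre-dose and 2 h for Cohort A. Cover SBP, DBP, pulse, QTcF, ventricular rate, QT, RR, PR and QRS, and body temperature wherever it was recorded at a scheduled time-point.
2. Add the same statistics for change from baseline by the 2.1.1.3 formula. The protocol does not name change explicitly; this goes slightly beyond restoring its text but uses a definition that the SAP already has.
3. Leave Cohort B post-baseline readings from discontinuation visits to the notable-value tables and listings, as SAP 5.3 requires.
4. State that the notable-value tables include the change-from-baseline rows of 5.5, shown separately from the absolute limits.
5. Itemise in Section 4 any protocol summary of vital signs or ECG that is still omitted.

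The cost is some SAP wording and two routine descriptive tables on data already collected, with no new assessments and no further children.

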2.6.2 Pharmacokinetic endpoints

Other pharmacokinetic variables of Fevipirant at steady state

The pharmacokinetic variables $T_{max,ss}$, $C_{min,ss}$, (CL/F)/kg, CL_r , amount and fraction of dose excreted over the PK collection interval of QAW039 at steady state will be secondary variables. All pharmacokinetic variables will be summarized similarly as mentioned for primary variable ([Section 2.5](#)).

Summary statistics for plasma and urine concentrations will be provided for cohort A by time point (only 1 time interval for urine). If any concentration value will be set to be zero for any time-point then Geo-mean, CV% geo-mean will not be presented for that time point.

Metabolite CCN362 at steady state

$C_{max,ss}$, $T_{max,ss}$, $AUC_{0-24h,ss}$, $C_{min,ss}$, CL_r , amount of dose excreted over the PK collection interval at steady state of CCN362, the major metabolite of fevipirant will be summarized similarly as mentioned for primary variable ([Section 2.5](#)).

Summary statistics for plasma and urine concentrations of analyte CCN362 will be provided for Cohort A by time point (only 1 time interval for urine). If any concentration value will be set to be zero for any time-point then Geo-mean, CV% geo-mean will not be presented for that time point.

2.7 Interim analysis

A planned interim analysis will be conducted to support decision making when 6 subjects (3 subjects from each of the 2 age strata) receiving 75 mg dose complete the treatment. The interim analysis will be performed based on preliminary PK data e.g. protocol times can be used to calculate PK parameters. At interim analysis, based on PK data from the 75 mg dose level the high dose will be chosen.

For detailed information, please refer to [Section 3](#).

3 Sample size calculation

Sample size is guided by statistical precision and requirements for pharmacokinetic data from pediatric subjects for inclusion in population PK modelling. Based on exploratory optimal design evaluation using modeling and simulation techniques, at least 12 subjects is expected to be sufficient for a pooled population PK analysis which is planned to be used to support dose selection for pediatric phase III studies. Since adult data on fevipiprant does not show a clinically relevant deviation from dose proportionality, data from the low and high dose cohort are equally valuable to inform the population PK model. Drop-outs and non-completers will be replaced.

At first stage it is required to have PK data from 6 subjects receiving 75 mg dose to assess safety, as well as mean and variability of PK data to enable at the second stage to have the right dose and number of subjects. Moreover, data from 6 subjects will provide ~80% probability for acceptable precision in calculating the geometric mean. More specifically, the inclusion of 6 subjects would result in the 95% confidence interval (CI) of the geometric mean of QAW039 AUC_{0-24h,ss} being in the range of (68%U, 147%U). U is the observed geometric mean, assuming a coefficient of variation of 31% based on data from previous study (QAW039A2111 study). This level of precision balances needs for reliable parameter estimation and clinical feasibility and is in agreement with guidance provided by health authorities. (General Clinical Pharmacology Considerations for Pediatric Studies for Drugs and Biological Products, FDA).

An interim analysis will be conducted when 6 subjects (3 subjects from each of two age strata) receiving the 75 mg dose will complete the treatment and provide the planned PK samples. At interim analysis, the following outcomes are foreseen based on AUC_{0-24h,ss}:

In terms of exposure i.e. mean AUC_{0-24h,ss}:

- 1) If mean AUC_{0-24h,ss} is as expected, i.e. comparable to 150 mg dose in adult/adolescents, then 225 mg dose will be used in high dose cohort. .
- 2) If mean AUC_{0-24h,ss} is relevantly more than expected while comparing with exposure of 150 mg dose in adult/adolescents, dose lower than 225 mg e.g. 150 mg dose will be used in high dose cohort.

3) If mean AUC0-24h,ss is relevantly less than expected while comparing with exposure of 150 mg dose in adult/adolescents, dose higher than 225 mg e.g. 300 mg or 375 mg dose will be used in high dose cohort.

In terms of variability i.e. coefficient of variation (CV%) of AUC0-24h,ss:

1) If CV% of AUC0-24h,ss is less than or equal to 31% at interim, then 6 subjects will be recruited for the second cohort so that total number of subjects completing treatment is 12.

2) If CV% of AUC0-24h,ss is more than 31% at interim analysis, more than 6 subjects will be recruited at the high dose level to provide ~80% probability for acceptable precision in calculating the geometric mean, more specifically to have the 95% confidence intervals (CI) of geometric means of QAW039 AUC0-24h,ss approximately within the range of (68%U, 147%U), where U is the observed geometric mean. The number of subjects on higher dose will be based on observed CV% at interim analysis.

The following table provides the range in which 95% CIs will fall with 80% probability in terms of percentage of observed geometric-mean, at different sample and different observed CV% at interim:

N (sample size)	Observed CV % at interim									
	35%	40%	45%	50%	55%	60%	65%	70%	75%	80%
7	69%- 146%	65%- 153%	62%- 161%	59%- 168%	57%- 176%	54%- 185%	52%- 193%	50%- 201%	48%- 209%	46%- 217%
8	71%- 140%	68%- 146%	65%- 153%	63%- 160%	60%- 166%	58%- 173%	56%- 180%	54%- 187%	52%- 194%	50%- 201%
9	74%- 136%	71%- 142%	68%- 147%	65%- 153%	63%- 159%	61%- 165%	59%- 171%	57%- 177%	55%- 183%	53%- 189%
10	75%- 133%	73%- 138%	70%- 143%	67%- 148%	65%- 154%	63%- 159%	61%- 164%	59%- 169%	57%- 175%	56%- 180%
11	77%- 130%	74%- 135%	72%- 140%	69%- 144%	67%- 149%	65%- 154%	63%- 159%	61%- 163%	59%- 168%	58%- 173%
12	78%- 128%	75%- 133%	73%- 137%	71%- 141%	69%- 146%	67%- 150%	65%- 154%	63%- 159%	61%- 163%	60%- 167%
13	79%- 127%	77%- 131%	74%- 135%	72%- 139%	70%- 143%	68%- 147%	66%- 151%	65%- 155%	63%- 159%	61%- 163%
14	80%- 125%	78%- 129%	75%- 133%	73%- 137%	71%- 140%	69%- 144%	68%- 148%	66%- 152%	64%- 155%	63%- 159%
15	81%- 124%	78%- 128%	76%- 131%	74%- 135%	72%- 138%	70%- 142%	69%- 145%	67%- 149%	66%- 152%	64%- 156%
16	81%- 123%	79%- 126%	77%- 130%	75%- 133%	73%- 136%	71%- 140%	70%- 143%	68%- 147%	67%- 150%	65%- 153%
17	82%- 122%	80%- 125%	78%- 128%	76%- 132%	74%- 135%	72%- 138%	71%- 141%	69%- 144%	68%- 147%	66%- 151%
18	83%- 121%	81%- 124%	79%- 127%	77%- 130%	75%- 133%	73%- 136%	72%- 140%	70%- 142%	69%- 145%	67%- 148%

For example, if we observe a CV% of 55% in the interim data, then 12 subjects are required to complete treatment with the high dose and to provide the planned PK samples to give ~80% probability for the 95% confidence intervals (CI) of geometric means of QAW039 AUC0-

24h,ss to fall approximately within the range of (68%U, 147%U). The sample size for the high dose can vary from 6 to 18 subjects, so that total number of subjects completing treatment (75 mg or high dose) and providing planned PK samples is maximum of 24. For example, if we observe a CV% of 80% in the interim data, then 18 subjects will be recruited at the high dose to provide the planned PK samples, though the 95% CI of geometric means of QAW039 AUC0-24h,ss will fall outside the range of (68%U, 147%U).

4 Change to protocol specified analyses

This statistical analysis plan is an abbreviated approach of presenting the limited data collected in the study and does not reflect the full analysis scope described in Section 12 of the study protocol (Version 01, Amendment 1 to original protocol released on 13-Feb-2019).

The following changes to the protocol specified analyses will be done:

- Definition of treatment emergent for safety adjusted: treatment end + 1 day will be replaced by treatment end date + 7 days for laboratory, vital signs, ECG and AEs, and to + 30 days for SAEs, to follow standard of QAW program.

5 Appendix

This appendix gives details about statistical methods in addition to the report text. All analyses will be performed by the most recent version of SAS available in the statistical programming environment.

